- Up to n=40 subjects with confirmed symptomatic SARS-CoV-2 infection, as determined by a documented positive polymerase chain reaction (PCR) test, and a positive antibody test at screening.
- Up to n=40 subjects with confirmed SARS-CoV-2 antibodies at screening or from an FDA-approved test as documented by the subject but with no history of symptoms.

This design will allow comparison between cohorts to explore the long-term immunological effects of SARS-CoV-2 infection. Recruitment in year 2 will be targeted toward these groups, and enrollment for each cohort will be stopped when its sample size is achieved for the year.

Because the vaccine response to the seasonal influenza vaccine in AA people has only started to be explored,¹⁰ we will recruit up to 10 AA subjects (of the 40) for each group described above in order to evaluate the relationship between AA race and vaccine responses in each of the three cohorts above.

Because obesity is associated with decreased vaccine responsiveness,¹¹ we will exclude individuals with a body mass index (BMI) ≥ 30 .

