15.2 Sample Size Justification

This is a hypothesis-generating study designed to examine relationships between different biomarkers measured at baseline and post-vaccination immune responses. To set the sample size, we used data from a previous study designed to examine biomarkers (09-H-0239).³ That study identified a significant relationship between $Y = \text{adjMFC}$ (a measure of vaccine-induced immune response adjusted for baseline response) and $X = \text{ID96_0}$ (a baseline readout of the frequency a $\text{CD38}^+ \text{CD20}^+$ memory B cell population). The estimated slope was 0.29 with an estimated standard error of $0.12 = \sqrt{\text{var}(R)/((n-1)*\text{var}(X))}$, where $\text{var}(R) = 2.09$ is the sample variance of the residuals from the regression line, $\text{var}(X) = 3.03$ is the sample variance of X , and $n = 49$ is the sample size of that study.

We used these estimates as a reference to set the sample size for the current study with the objective to identify a *new* biomarker that correlates with adjMFC with a similar or stronger relationship than was observed in 09-H-0239. We assumed the same error variance of $\text{var}(R) = 2.09$ and the same sample variance of $\text{var}(X) = 3.03$, and we assumed that the true slope is 0.29. We determined the power by using the Wald test where the slope is zero (i.e., the Wald test is $B/\text{se}(B)$ where B is the estimated slope and $\text{se}(B)$ is the estimated standard error). We assumed that this test is approximately standard normal under the null and approximately normal with mean $0.29/\sqrt{\text{var}(R)/((n-1)*\text{var}(X))}$ and variance 1 under the alternative.

We plan to correlate adjMFC with separate distinct collections of biomarkers (e.g., immune phenotyping as measured by flow cytometry or CyTOF, or RNA-seq). For each distinct collection, a multiplicity adjustment would be performed. Power calculations were performed (Table 2) considering various sample sizes, allowing for 5% missing data, and using a two-sided test with an alpha of 0.05 and with an illustrative Bonferroni adjustment for a moderate collection of biomarkers (50; e.g., nontrivial peripheral blood cell subsets measured by flow cytometry or CyTOF). With a sample size of 170 and 10% missing data, we have more than 80% power to identify biomarkers that have true slopes of 0.29 or better even with adjustment for 50 multiple comparisons.

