15.3 Description of the Analyses

The primary analysis will be to correlate multiple baseline biomarkers with the vaccine-induced outcome adjMFC using GEE to reflect clustering at the subject level due to multiple measurements over multiple years. Analyses will be stratified by year by including a separate term for each cohort year in the GEE models. Two-sided testing will be performed with an adjustment for multiplicity such as the Bonferroni to control the overall type I error rate at 0.05.

For the first secondary analysis, a similar analysis strategy will be used as in the primary analysis, but the relationship between the vaccine-induced outcome adjMFC and baseline biomarkers (specifically ID_96 [CD38⁺ CD20⁺ B cell frequencies and/or transcriptomic signatures]) and post-vaccination biomarkers (specifically ID_87 [plasmablast cell frequencies and/or transcriptomic signatures]) will be examined separately. Specifically, we will evaluate 1) whether the slope between adjMFC and ID96_0 (measured at day 0) is zero using GEE, as described for the primary analysis with no adjustment for multiplicity, and 2) whether the slope between adjMFC and ID_87, measured at day 7/day 0) is zero using GEE, as described for the primary analysis with no adjustment for multiplicity. Both analyses are designed to replicate findings from 09-H-0239.³

Analysis of the secondary endpoint on SARS-CoV-2 will involve comparing the results of the above analyses by cohort: 1) those subjects with prior symptomatic SARS-CoV-2 infection, 2) those subjects with prior asymptomatic SARS-CoV-2 infection, and 3) those subjects without a history of SARS-CoV-2 infection.

The exploratory analyses will involve both unsupervised and supervised analyses using the framework developed in 09-H-0239. In addition to that framework, under this protocol we will be able to characterize immune responses and biomarker relationships over multiple seasons in the same individual. The first general aim is to perform unsupervised analysis of the immune states of the baseline along the measured phenotypic dimensions, including PBMC/cell subset

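### Section 15.3 states no test of a difference between cohorts, in adjMFC or in slope, for the SARS-CoV-2 secondary endpoint

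*Combined protocol and SAP*

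**What the plan says.** Section 2.2 lists the effect of prior SARS-CoV-2 infection on the antibody response as a secondary objective. Section 3.2.2 gives the matching endpoint as a difference in titer response between previously infected subjects, with or without symptoms, and subjects with no evidence of infection. Section 3.1 sets up three year-2 cohorts of up to 40 each and says: "This design will allow comparison between cohorts to explore the long-term immunological effects of SARS-CoV-2 infection".

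The whole analysis of this endpoint in section 15.3 is one sentence naming the three cohorts: "Analysis of the secondary endpoint on SARS-CoV-2 will involve comparing the results of the above analyses by cohort". The analyses above it are:

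- the primary analysis, which relates adjMFC to many baseline biomarkers by GEE: "Two-sided testing will be performed with an adjustment for multiplicity such as the Bonferroni to control the overall type I error rate at 0.05";
- the first secondary analysis, which asks "whether the slope between adjMFC and ID96_0 (measured at day 0) is zero using GEE", and likewise for ID_87, each "as described for the primary analysis with no adjustment for multiplicity".

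For the cohort comparison the plan gives no cohort term, contrast, interaction, alpha or power. Section 15.1 does not mention the SARS-CoV-2 objective.

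**The concern.** The question is whether infection changes the response, so the relevant null is that the cohorts are equal. The stated tests, run by cohort, each have the null that the slope is zero in that cohort. A marker significant in one cohort and not in another is not evidence that the two differ, and with at most 40 subjects per cohort such splits can be common by chance. A correlate shared by everyone could then be reported as lost, or gained, after infection.

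There is a second gap. A slope of adjMFC on a biomarker, even if properly compared across cohorts, measures effect modification. Two cohorts can have identical slopes and very different mean adjMFC. The endpoint in section 3.2.2 is the difference in response, and no analysis of it is stated.

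**Working it through.** **Inputs.** From section 15.2: slope 0.29 ("and we assumed that the true slope is 0.29"), var(R) = 2.09, var(X) = 3.03, two-sided testing, and 0.05/50 = 0.001 for the illustrative 50 comparisons. From section 3.1: up to 40 per cohort. From Table 2: 10% missing, so 36 per cohort. Assumed: cohorts full and independent, one record per subject.

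**Plan's own figure.** se = sqrt(var(R)/((n-1) var(X))); power = Phi(0.29/se - z) + Phi(-0.29/se - z). At alpha 0.001 and n = 108, 153, 207, 252 this gives .626, .845, .957, .988. Table 2 has .63, .85, .96, .99, so it is reproduced.

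**One cohort.** At n = 36, se = sqrt(2.09/(35 x 3.03)) = 0.140 and 0.29/se = 2.07. Power is .542 at 0.05 and .110 at 0.001. At n = 40 and 0.05 it is .587.

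**Same slope in all three cohorts.** With power p per cohort, the chance that the three verdicts are not all alike is 1 - p^3 - (1-p)^3 = 3p(1-p). At p = .542 this is 3 x .542 x .458 = .745 (.727 with 40 per cohort). Simulation with per-cohort t tests gives 75% to 76% at n = 36. For any two cohorts the figure is 2 x .542 x .458 = .496.

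**One slope zero, two at 0.29.** Verdicts agree with probability .542^2 x .05 + .458^2 x .95 = .0147 + .1993 = .214, so they disagree 79% of the time by formula. Simulated, the figure is 76%.

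**Dependence on slope and alpha**, n = 36, same slope in all three cohorts:

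| Slope | Alpha | Power per cohort (formula) | Disagree, formula | Disagree, simulated |
|---|---|---|---|---|
| 0 | 0.05 | .05 | 14% | - |
| 0.29 | 0.05 | .542 | 74.5% | 75-76% |
| 0.45 | 0.05 | .894 | 28.5% | 36-37% |
| 0.58 | 0.05 | .985 | 4% | 10% |
| 0.29 | 0.001 | .110 | 29% | - |

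The two columns differ at steep slopes because the simulation uses t tests with estimated variance and a randomly drawn biomarker. With one slope set to zero, simulated disagreement is 94% for the 0.45 case and 95% for the 0.58 case.

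**Joint test on the same data.** A 2-df biomarker-by-cohort test rejects about 5% of the time when slopes are equal (4.9% to 5.1% simulated at n = 36). Its power is about 29-30% for slopes (0, 0.29, 0.29) at 0.05, about 3% at 0.001, and about 84% for (0, 0.58, 0.58) at 0.05.

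**Difference in mean adjMFC.** The plan gives no SD for adjMFC. Assume a range from sqrt(2.09) = 1.45 to sqrt(2.09 + 0.29^2 x 3.03) = 1.53. The pairwise difference detectable with 80% power is (1.96 + 0.84) x SD x sqrt(2/n). With 36 to 40 per cohort that is 0.63 to 0.66 SD, or about 0.91 to 1.01 adjMFC units.

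**The case against.** The strongest reply is that section 15.3 never says significance verdicts are what is compared. A GEE regression yields slopes and standard errors, and setting slopes and intervals side by side, or adding an interaction, also fits the wording. This stands: a reader might infer that the plan prescribes a comparison of verdicts, but the text does not say so, and the 75% is conditional on that reading. What remains is that the only results section 15.3 defines are tests of zero slope. Any other comparison is unspecified for a listed secondary endpoint and open to choice after the data are seen.

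A reader might also infer that equal cohorts look different 75% of the time in general. They do not. 3p(1-p) cannot exceed .75, and the planning slope at n = 36 happens to sit almost at that ceiling. Section 15.2 aims at relationships at least about as strong as the earlier study's, and at stronger slopes disagreement falls.

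A third tempting inference is that the comparison cannot show any effect of infection. That is too strong. At a slope of 0.58 even verdicts separate the cases, with 10% disagreement under equality against 95% when one slope is zero.

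Finally, the study describes itself as hypothesis-generating, cohort sizes are upper limits, and repeat seasons could raise power. These points lower the stakes. They do not supply a between-cohort test for an endpoint that has dedicated recruitment of up to 120 subjects.

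**Conclusion.** The concern holds in a limited form. No analysis stated in section 15.3 tests a difference between the SARS-CoV-2 cohorts, either in adjMFC, which is what the endpoint requires, or in biomarker slope. That follows from the text alone and needs no arithmetic.

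The size of the problem is conditional. If zero-slope verdicts are compared at the planning slope and unadjusted 0.05, they are split about as often when the cohorts are alike as when one has no association, so at that effect size the comparison is close to uninformative. This assumes full cohorts with 10% missing and one season per subject. With 20 to 30 analysed per cohort the equal-slope figure at 0.29 is 66% to 75%. It should not be quoted for other slopes or for the multiplicity-adjusted tests. The change is worth making because the remedy is cheap and also gives the endpoint an analysis.

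**What to change.** Replace the SARS-CoV-2 sentence in section 15.3 with a joint model on the year-2 cohorts:

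1. Regress adjMFC on cohort. Report the difference in mean adjMFC of each infected cohort from the no-history cohort, with 95% CIs, as the analysis of the endpoint, and state the alpha for these two contrasts.
2. For ID96_0, ID_87 and any markers carried over from the primary analysis, add biomarker and biomarker-by-cohort terms. Report the joint 2-df interaction test and each infected cohort's slope difference from the no-history cohort, with 95% CIs. Keep the primary multiplicity adjustment for the primary-analysis markers.
3. State that a difference in significance between cohorts will not be read as an effect of SARS-CoV-2.

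If later seasons of these subjects are included, say so and keep the GEE clustering by subject.

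The cost is a few sentences, one cohort model and one further model per marker, with no new subjects or samples. The drawback is low power for the slope comparisons at the planning slope, lowest under the multiplicity adjustment. Many will be inconclusive and should be presented as estimates with intervals.

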16.1 Informed Consent Process

Informed consent is a process where information is presented to enable persons to voluntarily decide whether or not to participate as a research subject. It is an ongoing conversation between the human research subject and the researchers which begins before consent is given and continues until the end of the subject's involvement in the research. Discussions about the research will provide essential information about the study and include: purpose, duration, experimental procedures, alternatives, risks, and benefits. Coercion and undue influence will be minimized by informing subjects that their decision to join the study will not affect any medical care they are currently receiving, or their eligibility to participate in other research studies at the NIH. Subjects will be given as much time as they need to read the consent form and ask questions of the investigators. Subjects will also be given time to discuss their participation with family members, friends, and other healthcare providers.

Informed consent will be obtained in person in a private setting by a study team member authorized to obtain consent. The subjects will sign the informed consent document prior to undergoing any research procedures. The subjects may withdraw consent at any time throughout

the course of the trial. A copy of the informed consent document will be given to the subjects for their records. The researcher will document the signing of the consent form in the subject's medical record. The rights and welfare of the subjects will be protected by emphasizing to them that the quality of their medical care will not be adversely affected if they decline to participate in this study.

16.2 Considerations for Consent of NIH Staff

Consent for NIH staff will be obtained as detailed above with following additional protections:

Consent from staff will be obtained by an individual independent of the staff member's team whenever possible. Otherwise, the consent procedure will be independently monitored by the CC Department of Bioethics Consultation Service in order to minimize the risk of undue pressure on the staff member.

16.3 Subject Confidentiality

All records will be kept confidential to the extent provided by federal, state, and local law. The study monitors and other authorized individuals may inspect all documents and records required to be maintained by the investigator, including but not limited to, medical records. Records will be kept locked and data will be coded. Any personally identifiable information maintained for this study will be kept on restricted-access computers and networks. Personally identifiable information will only be shared with individuals authorized to receive it under this protocol. Individuals not authorized to receive personally identifiable information will be provided with coded information only, as needed. Clinical information will not be released without written permission of the subject, except as necessary for monitoring by the IRB, NIAID, and the Office for Human Research Protections.

To further protect the privacy of study subjects, a Certificate of Confidentiality has been issued by the NIH. This certificate protects identifiable research information from forced disclosure. It allows the investigator and others who have access to research records to refuse to disclose identifying information on research participation in any civil, criminal, administrative, legislative, or other proceeding, whether at the federal, state, or local level. By protecting researchers and institutions from being compelled to disclose information that would identify research subjects, Certificates of Confidentiality help achieve the research objectives and promote participation in studies by helping assure confidentiality and privacy to subjects.

17 Data Handling and Record Keeping

17.1 Data Capture and Management

Study data will be maintained in CRIMSON and collected directly from subjects during study visits and telephone calls, or will be abstracted from subjects' medical records. Source

documents include all recordings of observations or notations of clinical activities and all reports and records necessary to confirm the data abstracted for this study. Data entry into CRIMSON will be performed by authorized individuals. The investigator is responsible for assuring that the data collected are complete, accurate, and recorded in a timely manner. Study data, including cumulative subject accrual numbers, should be generated via the chosen data capture method and submitted to the IRB as needed.

Appendix A. Schedule of Procedures/Evaluations

Evaluation	Study Day (window) ^a									
	Screening	Baseline	Vaccination	Follow-up						Optional Follow-up
	(-30 to -7)	-7 (± 2)	0	1 (± 0)	7 (± 0)	14 (± 1)	28 (± 2)	70 (± 2)	100 (± 7) ^b	Monthly ^c
Informed consent	X									
Clinical Procedures and Evaluations										
History, physical exam with height and weight (for BMI), and vital signs	X									
Electronic history/medication questionnaire		X ^d	X	X	X	X	X	X	X	X
Electronic AE questionnaire				X	X					
Vaccination			X ^e							
Stool collection (optional) ^f		X	X				X		X	
Clinical Laboratory Evaluations										
Blood Volume (mL)										
Urine/serum pregnancy test (women of childbearing potential)	4 ^g	4 ^d								
SARS-CoV-2 antibody	X									
CBC with differential	3 ^h	3 ^d	3	3	3	3	3	3	3	3
TBNK lymphocyte phenotyping	3 ^h	3 ^d	3	3	3	3	3	3	3	3
Acute care, mineral, and hepatic panels	4 ^h									
Anti-CMV IgG, IgM antibody and anti-EBV antibody panel	4 ^h									
Anti-HIV 1/2 antibody, antibody to hepatitis B surface antigen, and anti-hepatitis C virus antibody	8 ^h									
Research Laboratory Evaluations										
Blood Volume (mL)										
Serum isolation		4	4	4	4	4	4	4	4	4
PBMC isolation		60	90	40	40	40	40	40	40	40
Whole-blood RNA isolation		6	6	6	6	6	6	6	6	6
Daily Blood Volume	26	80	106	56	56	56	56	56	56	56
Cumulative Blood Volume	26	106	212	268	324	380	436	492	548	
Abbreviations: AE, adverse event; BMI, body mass index; CBC, complete blood count; CMV, cytomegalovirus; EBV, Epstein-Barr virus; HIV, human immunodeficiency virus; Ig, immunoglobulin; PBMC, peripheral blood mononuclear cell; RNA, ribonucleic acid; TBNK = T, B, and natural killer cells.										
^a After the first year of participation, subjects may repeat the study schedule annually through the 2023-24 influenza season. Screening will be repeated each year except the informed consent process and the history/physical exam/vital signs, which will be replaced with the electronic history/medication questionnaire. Subjects who are ineligible for that year will remain on study and may return to participate the following year if they are eligible.										
^b Subjects withdrawn before day 100 will be encouraged to have an early termination visit to complete procedures for the day 100 visit.										
^c Once per calendar month starting the calendar month after the day 100 visit, as requested up until 1 year following vaccination (up to 8 optional visits per year).										

^d To be performed if baseline is not the same day as screening.

^e Prior to vaccination, subjects will complete the history/medication questionnaire and blood draw, and will come to the clinic to review the questionnaire. After vaccination, subjects will be observed for AEs for 15 minutes. If there are no concerns about AEs after this period, subjects will be discharged.

^f Optionally, stool will be collected prior to vaccination (once at either day -7 or day 0), at day 28, and at day 100. Samples will be self-collected at the subject's domicile 24 hours before or after a study visit. Sampling kits with verbal and written instructions for collection will be provided to each subject prior to selected visits.

^g Unless performed at NIH within the previous 2 days.

^h Unless performed at NIH within the previous 30 days. Screening labs may be repeated at the discretion of the principal investigator within 30 days.

Appendix B. Electronic Study Questionnaires

Evaluation for Adverse Events: Days 1 and 7

Since receiving your flu vaccine, have you had any of the following symptoms?

	No	Yes (If yes, please specify one of the following.)			
Redness at the site of injection (2.5 cm or more)		2.5-5 cm	5.1-10 cm	More than 10 cm	Emergency room visit or hospitalization
Swelling or hardening at the site of injection (2.5 cm or more)		2.5-5 cm	5.1-10 cm	More than 10 cm	Emergency room visit or hospitalization
Pain at the site of injection		Does not interfere with daily activity	Repeated use of over-the-counter pain reliever OR interferes with some daily activity	Any use of prescription pain reliever OR prevents daily activity	Emergency room visit or hospitalization
Headache		Does not interfere with daily activity	Repeated use of over-the-counter pain reliever for more than 24 hours OR interferes with some daily activity	Any use of prescription pain reliever OR prevents daily activity	Emergency room visit or hospitalization
Fever (temperature above 100.4°F)		100.4-101.1°F	101.2-102.0°F	102.1-104°F	Over 104°F
Myalgia (body aches)		Does not interfere with daily activity	Interferes with some daily activity	Prevents daily activity	Emergency room visit or hospitalization
Any other symptoms? (If so, please describe):		Free Text			

Evaluation for Changes in Health History and Medications: Days -7, 0, 1, 7, 14, 28, 70, 100, and optional monthly visits

Since your last clinic visit, have you had any of the following changes?

	Yes	No
Started any new medications, including prescription or over-the-counter medications, vitamins, or herbal supplements?	If Yes, what? When? Dose?	
Stopped taking any medications, including prescription or over-the-counter medications, vitamins, or herbal supplements?	If Yes, what? When?	
Received any vaccinations?	If Yes, what? When?	
Had a blood transfusion?		
Had any surgical procedures?	If Yes, what?	
Had any symptoms of infections?	If Yes, what?	
Had any new medical diagnoses given to you by another health care provider?	If Yes, what?	
If female: Are you currently pregnant?		
Have you enrolled in or participated in any other research protocols since your last visit?	If Yes, what protocol?	

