8.1 Potential Risks

8.1.1 Study vaccine

The specific seasonal influenza vaccine used in this study will be determined by the NIH pharmacy (see section 5.3.1). Thus, the risks of the study vaccine will be the risks of either Flucelvax Quadrivalent, Fluvirin, or Fluzone High-Dose, which are described below.

Flucelvax Quadrivalent: In clinical trials, the most common (occurring in $\geq 10\%$ of subjects) local and systemic reactions in adults aged 18 through 64 years were injection site pain (45.4%), headache (18.7%), fatigue (17.8%) and myalgia (15.4%), injection site erythema (13.4%), and induration (11.6%). In adults 65 years and older, the most common reactions were injection site pain (21.6%) and injection site erythema (11.9%). In these populations, no reported serious AEs (SAEs) were assessed as being related to study vaccine.¹² Less common side effects include nausea, diarrhea, vomiting, loss of appetite, arthralgia, chills, malaise, ecchymosis, and fever.

There are insufficient data on the use of Flucelvax Quadrivalent in pregnant women to inform vaccine-associated risks in pregnancy. In a study using the trivalent formulation of Flucelvax in rabbits, there was no evidence of vaccine-related fetal malformations or variations and no AEs on pre-weaning development at a dose level about 11 times the human dose based on body weight.¹² Pregnant women are excluded from participation in this study.

Post-marketing reports include additional side effects such as extensive swelling of the injected limb.

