Fluvirin: In combined clinical trial data from the 1998-1999 season through the 2004-2005 season, in adults aged 18 through 64 years, the most common (occurring in $\geq 10\%$ of subjects) solicited local and systemic AEs within 96 hours after vaccination were associated with the injection site (e.g., pain, erythema, mass, induration, and swelling); the most common overall events were headache, fatigue, injection site reactions (pain, mass, erythema, and induration) and malaise. In adults 65 years and older in these same studies, the most common solicited local and systemic AEs were injection site pain and headache; the most common overall events were headache and fatigue.¹³ Other less common events across these studies included ecchymosis or pruritis at the injection site, pharyngitis, chills, sweating, shivering, nausea, arthralgia or myalgia, chest tightness or other breathing difficulties, coughing or worsening of existing cough, fever, rhinitis, or rhinorrhea.

Fluvirin can cause allergic reaction to individuals who are hypersensitive to eggs or egg products or other components of Fluvirin. Additionally, if Fluvirin prefilled syringes are used, the tip caps may contain natural rubber latex, which may cause allergic reactions in sensitive individuals. If

Fluvirin is used as the study vaccine, individuals with a history of allergy or sensitivity to any components of Fluvirin (including egg protein and, if prefilled syringes are used, latex) are excluded from participation in this study.

In post-marketing experience, hypersensitivity reactions have rarely led to anaphylactic shock and death. Other post-marketing reports include paralysis (e.g., Bell's Palsy), and skin reactions such as Stevens-Johnson syndrome.

Fluvirin is classified in Pregnancy Category B. There was no evidence of impaired fertility or harm to the fetus due to Fluvirin in a study in rabbits at a dose level about 15 times the human dose based on body weight.¹³ Pregnant women are excluded from participation in this study.

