Fluzone High-Dose: In clinical trials of subjects aged 65 years and older, the most common side effects were pain at the injection site, myalgia, malaise, and headache. In one trial of over 2,500 subjects aged 65 years and older, the most common reported events were injection-site pain (35.6%) and erythema (14.9%), and the most common solicited systemic AEs were myalgia (21.4%), malaise (18.0%), and headache (16.8%). Other reported events included injection-site swelling and fever.¹⁴

Fluzone High-Dose can cause allergic reaction (including anaphylaxis) to individuals who are hypersensitive to any component of the vaccine, including egg protein, or to individuals who have had allergic reactions to previous doses of influenza vaccination. For subjects aged 65 years and older, because Fluzone High-Dose will be used as the study vaccine, individuals with a history of allergy or sensitivity to any components of this vaccine are excluded from participation in this study.

In post-marketing experience, individuals receiving Fluzone High-Dose have reported anaphylaxis and other hypersensitivity reactions (including urticaria and angioedema), facial palsy (Bell's Palsy), and skin reactions such as Stevens-Johnson syndrome.

Influenza vaccines in general: The following risks may be possible with either Flucelvax Quadrivalent, Fluvirin, or Fluzone High-Dose.

GBS is a theoretical risk of influenza vaccinations. Evidence for a causal relation of GBS with other influenza vaccines is inconclusive; if an excess risk exists, it is probably slightly more than 1 additional case per 1 million persons vaccinated.^{12,13} Individuals with a history of GBS are excluded from participation in this study.

Allergic reactions to the influenza vaccine are possible, and during post-marketing surveillance, serious allergic reactions (e.g., anaphylactic shock) have been observed in individuals receiving

either study vaccine. Additionally, syncope is possible following injected vaccines and may be accompanied by transient neurological signs (e.g., visual disturbance, paresthesia, and tonic-clonic limb movements). Subjects will be monitored for these reactions as described in section 5.3.2.

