12.2 Recording/Documentation

AEs related to the study vaccine will be recorded for 7 days after vaccination. AEs from other research procedures (i.e., blood draw) that occur within 24 hours after the procedure will also be recorded. AEs will be recorded and reviewed in a timely manner by the research team and reported as outlined below. The start date, the stop date, the severity of each reportable event, and the PI’s judgment of the AE’s relationship and expectedness to the study agent/intervention will also be recorded in the Clinical Research Information Management System of the NIAID (CRIMSON).

Expected events are described in section 8.1 and the package inserts.^{12,13} Events will not be reported unless they are Grade 3 or greater or occur at a severity or frequency greater than expected, at which time they will be reported as UPs.

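### Fatigue and malaise have no row on the adverse-event questionnaire, so the section 12.2 comparison with expected frequency is unreliable for these two symptoms

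*Combined protocol and SAP*

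**What the plan says.** The Appendix B questionnaire for days 1 and 7 opens with "Since receiving your flu vaccine, have you had any of the following symptoms". It then names redness, swelling or hardening, injection-site pain, headache, fever and "Myalgia (body aches", each with graded answers. The last row is "Any other symptoms? (If so, please describe", answered in free text with no severity options.

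For Flucelvax Quadrivalent at age 18 to 64, section 8.1.1 lists "headache (18.7%), fatigue (17.8%) and myalgia (15.4" (percentages) among the reactions seen in at least 10% of subjects. For Fluzone High-Dose it says that "the most common solicited systemic AEs were myalgia (21.4%), malaise (18.0%), and headache (16.8" (percentages). For Fluvirin at age 18 to 64 it counts both fatigue and malaise among the most common overall events, without individual rates.

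Section 12.2 takes expected events from section 8.1 and the package inserts. Events are reported only if they are Grade 3 or greater or "occur at a severity or frequency greater than expected". No numerical threshold is given. Section 7.1 adds that a positive answer on the questionnaire prompts a telephone call from the study team.

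**The concern.** A rule based on excess frequency needs an observed count collected in roughly the same way as its benchmark. Headache and myalgia are asked about by name, with grades. Fatigue and malaise, with expected rates of similar size, depend on the subject thinking to write them down or mention them in a call. For malaise with Fluzone High-Dose the mismatch is explicit, because the benchmark is a solicited rate. The reference numbers attached to the package inserts in section 12.2 are those for Flucelvax and Fluvirin only, so section 8.1 is the only benchmark cited there for Fluzone High-Dose.

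If the observed count is too low, a real excess of a mild or moderate symptom can look ordinary and go unreported.

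**Working it through.** **1. The form against the benchmark.**

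| Vaccine (recipients in this study) | Fatigue in section 8.1.1 | Malaise in section 8.1.1 |
|---|---|---|
| Flucelvax Quadrivalent (under 65) | 17.8% at age 18 to 64 | listed as less common |
| Fluvirin (under 65) | among the most common overall events at 18 to 64, no rate | same |
| Fluzone High-Dose (65 and older) | not named | 18.0%, solicited |

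For each vaccine at least one leading systemic reaction has no row. Symptoms of similar frequency do have rows: headache (18.7% and 16.8%) and myalgia (15.4% and 21.4%) for Flucelvax and Fluzone High-Dose respectively. Low frequency does not explain the choice, because fever has a row although section 8.1.1 lists it as less common for both Flucelvax and Fluvirin.

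**2. Average effect of incomplete capture.** The plan gives no figure for this rule, so there is nothing to reproduce. Let n be the number vaccinated, p the expected rate, k the true excess factor and c the fraction of cases that reach the record. The benchmark count is n × p and the average observed count is n × p × k × c. The second is no larger than the first when c ≤ 1/k:

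- 1.5-fold excess: hidden on average if c ≤ 0.67
- doubling: c ≤ 0.50
- tripling: c ≤ 0.33

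As an illustration, take n = 120 (the year 2 ceiling, assumed all on Flucelvax) and p = 0.178. The benchmark is 120 × 0.178 = 21.4 cases. A true doubling gives 120 × 0.356 = 42.7. With c = 0.50 the record shows 21.4, and with c = 0.25 it shows 10.7.

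**3. Probability of noticing the excess.** This needs a meaning for greater than expected. Assume a flag at the smallest count r with P(X ≥ r) ≤ 0.025 for X binomial(n, p). For n = 120 and p = 0.178, r = 31 (false-flag probability 0.018). The probability of a flag is then P(X ≥ 31) with X binomial(120, 0.178 × k × c):

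| True excess | c = 1 | c = 0.75 | c = 0.50 | c = 0.25 |
|---|---|---|---|---|
| 1.5-fold | 0.62 | 0.07 | about 0 | about 0 |
| 2-fold | 0.99 | 0.62 | 0.02 | about 0 |
| 3-fold | about 1 | about 1 | 0.62 | about 0 |

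With p = 0.180, as for malaise, and the same n, a doubling is flagged with probability 0.99, 0.65, 0.02 and about 0. With n = 170 and p = 0.178 (flag at 41 or more) the values for a doubling are about 1, 0.80, 0.02 and about 0. With n = 24 (flag at 9 or more) a doubling is flagged with probability only 0.50 even at full capture.

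**The case against.** A reader might infer that section 12.2 cannot work at all for fatigue and malaise, or that the free-text box is the only way in. The documents support neither reading. Every subject is asked an open question on both days, which is more than waiting for spontaneous reports. Any positive answer prompts a call (section 7.1), and injection-site pain alone is expected in 45.4% of adults aged 18 to 64 on Flucelvax. Days 1 and 7 are clinic visits (section 6.4), and section 17.1 allows data to be collected at visits and by telephone. Section 12.2 records vaccine-related events for 7 days without limiting them to the named rows. The investigator grades every event on a stated toxicity scale (section 12.1), so a free-text entry need not stay ungraded. All of this stands. It does not close the gap: the call is not described as asking about unlisted symptoms, and a subject with fatigue alone who leaves the box empty triggers no call.

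A reader might also rely on the Fluvirin sentence that "the most common overall events were headache and fatigue". It describes adults 65 and older, who receive Fluzone High-Dose in this study. The sentence for age 18 to 64 is the relevant one.

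The illustration has limits too. The 120 is a ceiling, there is no upper age limit, Fluvirin is an alternative under 65, and the number of Fluzone High-Dose recipients is not given. Because section 12.2 sets no threshold, the rule is imprecise for headache and myalgia as well, and new rows would not change that.

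The stakes are modest. The vaccines are licensed and none of the listed endpoints is a safety endpoint. The pausing rule (section 12.5) uses Grade 3 or higher unexpected related events or the investigator's judgement, and the halting rule (section 12.6) uses that judgement alone.

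**Conclusion.** The frequency comparison in section 12.2 is unreliable for fatigue and malaise, not inoperable. The direction of the bias is clear for malaise with Fluzone High-Dose, where a count from an open question is set against a solicited rate. It is likely for fatigue with Flucelvax, though section 8.1.1 does not say how that rate was collected. For Fluvirin there is no rate in section 8.1.1 to compare with.

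The size depends on the capture fraction, which is assumed throughout. Under the assumed flag with 120 subjects, a doubling goes from almost certain detection (0.99) to almost none (0.02) as capture falls from all cases to half. A tripling at half capture is still flagged with probability 0.62. Grade 3 reporting involves no frequency comparison, although the symptom must still be mentioned. The primary endpoint is unaffected. This is a worthwhile improvement to the form rather than a serious fault.

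**What to change.** Add two rows to the day 1 and day 7 questionnaire in Appendix B, Fatigue (tiredness) and Malaise (feeling generally unwell), using the severity columns already used for myalgia. This needs no new visit, procedure or grading scale.

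The cost is more positive responses and so more follow-up calls, and fatigue and malaise counts that are not comparable with seasons already collected. Any summary across seasons should mark the change. If the sponsor prefers to leave the form alone, section 12.2 should say that the frequency comparison covers only the symptoms asked about by name.
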